### 3. List of Acronyms and Abbreviations

Acronym/ Abbreviation	Expanded Term
AAD	Antiarrhythmic Drug
ACC/AHA	American College of Cardiology/American Heart Association
ACE	Asymptomatic Cerebral Emboli
ACT	Activated Clotting Time
AE	Adverse Event
AEF	Atrio Esophageal Fistula
AF	Atrial Fibrillation
AFEQT	Atrial Fibrillation Effect on Quality of Life
AFL	Atrial Flutter
AT	Atrial Tachycardia
CA	Competent Authority
CABG	Coronary Artery Bypass Graft
CHF	Congestive Heart Failure
COPD	Chronic Obstructive Pulmonary Disease
CPK	Creatinine Phosphokinase
CRF	Case Report Form
CRO	Clinical Research Organization
CS	Coronary Sinus
CSR	Clinical Study Report
CT	Computed Tomography
CTI	Cavotricuspid Isthmus
CVA	Cerebrovascular Accident or Stroke
DM	Diabetes Mellitus
DMC	Data Monitoring Committee
EB	Ethics Board
EC	Ethics Committee
ECG	Electrocardiogram
eCRF	Electronic Case Report Form
EDC	Electronic Data Capture
EHRA AF	European Heart Rhythm Association Atrial Fibrillation
EMEA	Europe, Middle East and Africa
EP	Electrophysiology
ESC	European Society of Cardiology
FAM	Fast Anatomical Mapping
FDA	Food and Drug Administration
Fr	French
FU	Follow-Up
GCP	Good Clinical Practices

Acronym/ Abbreviation	Expanded Term
GERD	Gastroesophageal Reflux Disease
GSMC	Global Safety Monitoring Committee
HM	Holter Monitoring
HRS/EHRA/ECAS	Heart Rhythm Society / European Heart Rhythm Association / European Cardiac Arrhythmia Society
ICE	Intracardiac Echocardiography
ICF	Informed Consent Form
ICH	International Conference on Harmonization
IFU	Instruction for Use
ILR	Implantable Loop Recorder
IRE	Irreversible Electroporation
ITT	Intention to Treat
LA	Left Atrium
LBBS	Left Bundle Branch Block
LV	Left Ventricle
LVEF	Left Ventricular Ejection Fraction
MEDDEV	Medical Device Directive Guidance
MDD	Medical Device Directive
MDR	Medical Device Regulation
MI	Myocardial Infarction
mITT	Modified Intent to Treat
MMSE	Mini Mental State Examination
MRA	Magnetic Resonance Angiogram
MRI	Magnetic Resonance Imaging
mRS	Modified Rankin Scale
NAE	Neurological Assessment Evaluable
NIHSS	National Institute of Health Stroke Scale
NYHA	New York Heart Association
PAF	Paroxysmal Atrial Fibrillation
PFA	Pulsed Field Ablation
PFE	Pulsed Field Energy
PI	Principal Investigator
PN	Phrenic Nerve
PNP	Phrenic Nerve Paralysis
PP	Per Protocol
PPI	Proton Pump Inhibitors
PSU	Power Supply Unit
PV	Pulmonary Vein
PVI	Pulmonary Vein Isolation
QA	Quality Assurance

Acronym/ Abbreviation	Expanded Term
QC	Quality Control
QoL	Quality of Life
RA	Right Atrium
RF	Radiofrequency
RFCA	Radiofrequency Catheter Ablation
RV	Right Ventricle
SADE	Serious Adverse Device Effect
SAE	Serious Adverse Event
SAP	Statistical Analysis Plan
SDV	Source Data Verification
SOC	Standard Of Care
SP	Safety Population
SVC	Superior Vena Cava
TEE	Transesophageal Echocardiography
TIA	Transient Ischemic Attack
TS	Transseptal
TTE	Transthoracic Echocardiography
UADE	Unanticipated Adverse Device Effect
UM	User Manual
USADE	Unanticipated Serious Adverse Device Effect

**CONTACTS:**

Whereas, the Clinical Study is sponsored by Biosense Webster Inc., Johnson and Johnson Medical NV/SA with registered offices at [name], has been duly appointed by the Sponsor to conduct the Clinical Study on its behalf.

The sponsor maintains an updated list of Principal Investigators (PIs), the coordinating investigator (if appointed), address details of each investigational site, emergency contact details for the PI's at each site, roles and responsibilities and qualifications of each respective investigator, institutions,

corelabs (if applicable) and Contract Research Organizations (if applicable). The definitive list shall be integrated into the study report.

The current protocol has been developed based on regulations applicable in Europe, for countries outside Europe, a country specific version of this study protocol may be developed, further defining regional regulations, if applicable.

	
[REDACTED]

Premarket or Post market	Premarket
Study Design	
Prospective, single arm, multi-center, pre-market clinical evaluation of the IRE system (Circular IRE Catheter and IRE Generator) to demonstrate safety and long-term effectiveness when compared to a performance goal based on a historical control.
 
The study shall include two sequential waves:
 
Wave I of the study will enroll up to 40 subjects, who will undergo the index procedure and additional neurological, PV and esophageal assessments.
 
Wave II of the study will enroll roll-ins, and up to 330 subjects in the main phase. Wave II subjects will undergo the index procedure and same follow-up schedule as Wave I subjects, excluding the additional neurological, and post procedural PV (unless symptomatic) and esophageal assessments.
 
Bayesian adaptive design will be used for sample size selection in Wave II of the study.

Sample Size	
As Wave I of the study is a safety characterization phase, a sample size of 40 subjects is intended to delineate safety and provide preliminary estimates for safety and acute effectiveness of the IRE system.
 
Two sample size selection interim analyses will be performed in Wave II. Predictive probabilities of success will be used to determine whether the enrollment will be stopped or continued at each sample size selection interim analysis. The study may enroll up to a maximum of 330 subjects in the main phase.

Study Population	Patients scheduled to have a clinically-indicated ablation procedure for the management of their drug refractory PAF will be screened for enrollment per the study's inclusion and exclusion criteria.
Geographic areas to be included	Up to 30 sites mainly in Europe and possible other regions.

Anticipated Study Timeline
	
Total duration: Approximately 17 months of enrollment: Wave I: 4 months in a maximum of 7 sites Wave II: 13 months in a maximum of 30 sites + 12 months Follow-Up (FU)
												

Procedure(s) description
	
Subjects will arrive to the electrophysiology (EP) laboratory for their ablation procedure and will undergo preparation for the procedure per the hospital's standard protocol (discretion of investigator).
 
The AF Ablation procedure will follow below sequence:
 
 
1. Anatomical mapping of the LA
 
2. PVI using the study catheter
 
3. Confirmation of PV isolation (entrance block) with adenosine/isoproterenol challenge
 
4. If necessary, treatment of acute reconnections with additional applications of PFA energy
 
5. Confirmation of entrance block of all targeted PVs
 
 
In this study protocol, IRE ablation modality is to be used as the primary mode for PVI. If PVI cannot be achieved with PFA, the IRE system should be disconnected prior to use of a commercial Radiofrequency (RF) system, to complete the procedure.
 
The Circular IRE Catheter should not be used for lesions outside the PV region
												

Primary Objective
	
The primary objective of this clinical investigation is to demonstrate safety and long-term effectiveness of the IRE system (Circular IRE Catheter and IRE Generator) when used for isolation of the atrial PVs in treatment of subjects with PAF.
												

Primary Endpoints
	
Only Wave II subject data will be used for the purpose of primary hypothesis testing. Wave I and roll-in subject data will be separately analyzed (not part of the primary hypothesis testing).
 
Acute Safety
 
The primary safety endpoint is the incidence of Primary Adverse Events (PAEs) (within seven (7) days of the initial mapping and ablation procedure). PAEs include the following Adverse Events (AEs):
 
 
 Atrio-Esophageal Fistula*	Phrenic Nerve Paralysis (permanent)	
 
 Cardiac Tamponade/perforation	Pulmonary Vein Stenosis*	
 
 Device or procedure related death*	Stroke/CVA	
 
 Major Vascular Access Complication/Bleeding	Thromboembolism	
 
 Myocardial Infarction	Transient Ischemic Attack (TIA)	
 
 Pericarditis		
 
 
* Device or procedure related death, pulmonary vein stenosis and atrio-esophageal fistula that occur greater than one week (7 days) post-procedure are considered and analyzed as PAEs.
	Atrio-Esophageal Fistula*	Phrenic Nerve Paralysis (permanent)	Cardiac Tamponade/perforation	Pulmonary Vein Stenosis*	Device or procedure related death*	Stroke/CVA	Major Vascular Access Complication/Bleeding	Thromboembolism	Myocardial Infarction	Transient Ischemic Attack (TIA)	Pericarditis	
Atrio-Esophageal Fistula*	Phrenic Nerve Paralysis (permanent)												
Cardiac Tamponade/perforation	Pulmonary Vein Stenosis*												
Device or procedure related death*	Stroke/CVA												
Major Vascular Access Complication/Bleeding	Thromboembolism												
Myocardial Infarction	Transient Ischemic Attack (TIA)												
Pericarditis													

	
Long term effectiveness Freedom from documented (symptomatic and asymptomatic) atrial arrhythmia (Atrial Fibrillation (AF), Atrial Tachycardia (AT) or Atrial Flutter (AFL)) episodes based on electrocardiographic data (<math>\geq 30</math> seconds on arrhythmia monitoring device) during the effectiveness evaluation period (Day 91-Day 365). Acute procedural failure (i.e., failure to confirm entrance block, with or without touch-up, in all PVs except those that are silent and/or cannot be cannulated post-procedure) will be considered a long-term effectiveness failure.


Secondary Endpoints
	
 
- Acute Procedural Success defined as confirmation of entrance block in all clinically relevant targeted PVs after adenosine/ isoproterenol challenge. Use of a non-study catheter to achieve PVI is considered an acute procedural success failure.
 
- Freedom from documented symptomatic atrial arrhythmia (AF, AT or AFL) episodes based on electrocardiographic data (<math>\geq 30</math> seconds on arrhythmia monitoring device) during the effectiveness evaluation period (Day 91-Day 365).
 
- Quality of Life (QoL): the change of QoL assessed by comparing the Atrial Fibrillation Effect on Quality-of-Life (AFEQT™) scores before and after the ablation procedure.
 

Additional Endpoints
	
Safety
 
 
- Occurrence of individual PAEs from the primary composite
 
- Occurrence of Serious Adverse Device Effects (SADEs)
 
- Occurrence of Serious Adverse Events (SAEs) within 7 days (early-onset), 8-30 days (peri-procedural) and >30 days (late onset) of initial ablation procedure
 
- Occurrence of non-SAEs
 
- Occurrence of clinically symptomatic severe PV stenosis as documented by CT/MRA
 
 
Effectiveness
 
 
- Ablation by a non-study catheter for PVI (touch-up) among all clinically relevant targeted PVs and by subject
 
- Acute reconnection identified by adenosine/isoproterenol challenge. among all clinically relevant targeted PVs and by subject
 
- % repeat ablation within the 12M FU period             
 
o Timing (blanking period or after blanking)
 
o % PV reconnection
 
 
 
- Freedom from documented symptomatic and asymptomatic atrial fibrillation (AF) episodes based on electrocardiographic data (<math>\geq 30</math> seconds on arrhythmia monitoring device) during the effectiveness evaluation period (Day 91-Day 365).
 
- Freedom from documented (symptomatic and asymptomatic) atrial arrhythmia (AF, AT or AFL) episodes based on electrocardiographic data (<math>\geq 30</math> seconds on arrhythmia monitoring device) during the effectiveness evaluation period (Day 91-Day 365) with the following criteria also deemed failure:
 

	
 
○ Taking a new class I/III Antiarrhythmic Drug (AAD) for AF or a previously failed class I/III AAD at a greater than the highest ineffective historical dose for AF during the effectiveness evaluation period
 
○ Greater than 2 repeat ablations for AF/AT or AFL in the blanking period or any repeat ablation for AF/AT or AFL during the effectiveness evaluation period
 
 
Procedural data, including but not limited to
 
 
- Total procedure time
 
- Mapping time
 
- PFA application time
 
- Number of PFA applications by PV and by subject
 
- Total fluoroscopy time
 
- Study catheter dwell time
 
- Ablation settings used
 
- Use of paralytics and anesthesia
 
 
Neurological Assessment (Wave I)
 
 
- Occurrence of new post-ablation asymptomatic and symptomatic cerebral emboli as determined by Magnetic Resonance Imaging (MRI) evaluations
 
- Occurrence of new or worsening neurological deficits post-ablation and at follow-up, compared to baseline
 
- Occurrence, anatomical location and size of asymptomatic and symptomatic cerebral emboli observed pre-and post-ablation as determined by MRI evaluations.
 
- Summary of Mini Mental State Examination (MMSE), National Institute of Health Stroke Scale (NIHSS) and Modified Rankin Scale (mRS) at baseline, post-ablation and during follow-up (if lesions were identified in prior evaluation)
 
 
CT/MRA (Wave I)
 
 
- Occurrence of severe PV stenosis at 3 months post-ablation as determined by Computed Tomography (CT)/ Magnetic Resonance Angiogram (MRA) evaluations.
 
 
Endoscopy (Wave I)
 
 
- Occurrence of post-ablation esophageal lesions as determined by post-procedure endoscopy
 

Inclusion Criteria	
 
1. Diagnosed with Symptomatic PAF.
 
2. Selected for AF ablation procedure by PVI.
 
3. Failed at least one AAD (class I to IV) as evidenced by recurrent symptomatic AF, or intolerable or contraindicated to the AAD.
 
4. Age 18 -75 years
 
5. Willing and capable of providing consent
 
6. Able and willing to comply with all pre-, post-, and follow-up testing and requirements
 

Exclusion Criteria	
 
1. AF secondary to electrolyte imbalance, thyroid disease, or reversible or non-cardiac cause.
 
2. Previous LA ablation or surgery
 

	

3. Patients known to require ablation outside the PV region (e.g. CTI region, atrioventricular reentrant tachycardia, atrioventricular nodal reentry tachycardia, atrial tachycardia, ventricular tachycardia and Wolff-Parkinson-White).

4. Previously diagnosed with persistent AF (> 7 days in duration)

5. Severe dilatation of the LA (LAD >50mm antero-posterior diameter in case of Transthoracic Echocardiography (TTE))

6. Presence of LA thrombus

7. Severely compromised LVEF (LVEF <40%)

8. Uncontrolled heart failure or New York Heart Association (NYHA) Class III or IV

9. History of blood clotting, bleeding abnormalities or contraindication to anticoagulation (heparin, warfarin, or dabigatran)

10. History of a documented thromboembolic event (including TIA) within the past 6 months

11. Previous PCI/MI within the past 2 months

12. Coronary Artery Bypass Grafting (CABG) in conjunction with valvular surgery, cardiac surgery (e.g. ventriculotomy, atriotomy) or valvular cardiac (surgical or percutaneous) procedure.

13. Unstable angina pectoris within the past 6 months

14. Anticipated cardiac transplantation, cardiac surgery or other major surgery within the next 12 months.

15. Significant pulmonary disease (e.g., restrictive pulmonary disease, constrictive or chronic obstructive pulmonary disease) or any other disease or malfunction of the lungs or respiratory system that produces severe chronic symptoms

16. Known significant PV anomaly that in the opinion of the investigator would preclude enrollment in this study

17. Has known pulmonary vein stenosis

18. Acute illness, active systemic infection or sepsis

19. Presence of intracardiac thrombus, myxoma, tumor, interatrial baffle or patch or other abnormality that precludes catheter introduction or manipulation.

20. Severe mitral regurgitation

21. Presence of implanted pacemaker or Implantable Cardioverter-Defibrillator (ICD) or other implanted metal cardiac device that may interfere with the IRE energy field.

22. Presence of a condition that precludes vascular access (such as IVC filter)

23. Significant congenital anomaly or a medical problem that in the opinion of the investigator would preclude enrollment in this study

24. Categorized as vulnerable population and requires special treatment with respect to safeguards of well-being

25. Current enrollment in an investigational study evaluating another device or drug.

26. Women who are pregnant (as evidenced by pregnancy test if premenopausal), lactating, or who are of child bearing age and plan on becoming pregnant during the course of the clinical investigation.

27. Life expectancy less than 12 months

--	---

	
28. Presenting contra-indications for the devices used in the study, as indicated in the respective Instructions For Use (IFU)
 
Additional exclusion criteria for Wave I subjects:
 
29. Contraindication for MRI such as use of contrast agents due to advanced renal disease, claustrophobia etc. (at PI discretion)
 
30. Presence of iron-containing metal fragments in the body
 
31. Unresolved pre-existing neurological deficit.
 
32. Uncontrolled significant GastroEsophageal Reflux Disease (GERD)

Safety Assessments
	
The safety endpoint is the incidence of early onset Primary Adverse Events (PAEs) (within seven (7) days of the initial ablation procedure).
 
Additional safety assessments on neurological lesions, esophageal lesions and PV stenosis will be performed for the Wave I subjects.

Statistical Analysis
	
The main phase of the study (Wave II) will use a Bayesian adaptive design to determine the sample size. The timing of sample size selection interim analyses will be described in the Statistical Analysis Plan (SAP). A maximum of 330 subjects may be enrolled in the main study phase. An additional interim analysis will be performed for claiming early trial success when 30 subjects reach full 12-month of follow-up and all subjects in three months of follow-up. If the criteria for early success are met, filing for CE Mark will be performed while 12-month follow-up is ongoing in the remaining subjects.
 
Final Primary safety analysis
 
The final analysis for the primary safety endpoint will use a beta-binomial model with a non-informative uniform prior. The endpoint will be considered a success if the posterior probability of the safety rate being less than 14% is greater than 0.975.
 $H_0: \Pr(P_s < 0.14) \leq 0.975$ $H_a: \Pr(P_s < 0.14) > 0.975$ 
Final Primary effectiveness analysis
 
The final analysis for the primary effectiveness endpoint will use a beta-binomial model with a non-informative uniform prior. The endpoint will be considered a success if the posterior probability of the primary effectiveness success rate being greater than 50% is greater than 0.9775.
 $H_0: \Pr(P_E > 0.50) \leq 0.9775$ $H_a: \Pr(P_E > 0.50) > 0.9775$

Interim Analysis	Detailed information on analysis performed within the study will be described in the statistical Analysis plan. Sample size selection analysis and an interim analysis for claiming early trial success will be performed.
Determination if DSMB/DMC/CEC required	DMC and CEC will be established for this study 

- DMC will assess subjects' data for safety on regular intervals for Wave I and Wave II and make recommendations on study adaptations.

- CEC will adjudicate primary safety endpoint events for Wave I and Wave II.

Time and Events Schedule	See table 1 below

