the 2017 HRS/EHRA/ECAS/APHRS/SOLAECE Expert Consensus Statement on Catheter and Surgical Ablation of AF. Data from large multicenter pre and post-market clinical trials of AF ablation devices which were published between 2014 to 2019 were reviewed as a first step to deriving the performance goal for the safety endpoint. A meta-analysis approach was taken to estimate the average composite endpoint rate. The following trials were reviewed: Fire & Ice, Heartlight, TOCCASTAR^45, ZERO-AF, and SMART-AF. These trials are representative of different catheter designs and energy sources. Since the definition of the safety composite varies across the studies reviewed, individual complication rates were reviewed and utilized to derive composite rates from each trial that are more closely aligned with the proposed primary safety composite endpoint definition. The meta-analysis yielded a composite primary safety endpoint rate of 7% (95% UCB: 8%). A margin of indifference of 6 percentage points was utilized to set the PG of 14%.

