## 8.2 Study Endpoints

Only Wave II subject data will be used for the purpose of primary hypothesis testing. Wave I and roll-in subject data will be separately analyzed (not part of the primary hypothesis testing), further described in the statistical section of this protocol (section 20).

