**At 1, 3, 6 and, 12-month follow-up visits, the following assessments will be performed:**

- Medical evaluation:
  - AEs
  - Cardiac and Anti-coagulation medication regimen
  - Cardiac related hospitalization and cardioversions
  - 12 Lead-ECG (if completed per standard of care)

- **Atrial arrhythmia monitoring as from month 3 (non-SOC)**
  - Remote Monitoring:  
Subjects will be provided with a remote monitoring device at the 3M FU visit and asked to record and transmit a minimum of 1 transmission ( $\geq 30$  seconds) every week through the end of the month 5 of FU. Starting at month 6 of FU, subjects will be asked to record and transmit a minimum of 1 transmission ( $\geq 30$  seconds) every month until the effectiveness evaluation period is completed (12 months post index procedure). Subjects will also be asked to transmit any symptom-triggered episode that occurs from the time they receive the remote monitoring device through the 12M FU visit. A core lab might be used to evaluate and assess the remote monitoring tracings.  
  
Remote monitoring will be conducted as follows:
    - Distribution and start by month 3
    - <6M: Weekly transmission of at least 1 scheduled recording
    - $\geq 6M$ : Monthly transmission of at least 1 scheduled recording
    - Conduct and transmit recording whenever symptoms are present
  - 24 Hour Holter:  
Holter monitor will be used at each follow-up visit to monitor the subjects' heart rhythm for 24 hours continuously. Following the 24h Holter, subjects will be contacted by the site to verify if symptoms are experienced during 24h Holter.
- Quality of life via the **Atrial Fibrillation Effect on Quality-of-Life (AFEQT™)** questionnaire (non-SOC), at Month 3, 6 and 12. Note: Patient questionnaires will only be used in countries with validated languages.
- **Cardiac CT/MRA**
  - **Wave I subjects:** is required to be performed at the 3M FU visit (non-SOC) or any other point in time when subject presents with symptoms of PV stenosis.
  - **Wave II subjects:** is only required to be performed if subject presents with symptoms of PV stenosis.
- **Wave I subjects only: Cerebral MRI, Neurological Exam and Neurological Evaluation using the MMSE, NIHSS and mRS (non-SOC)** are required to be performed if any neurological symptoms and/or cerebral ischemic lesions were identified at a prior evaluation. Note: Patient questionnaires will only be used in countries with validated languages.

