#### **14.6 Core Laboratory for Evaluation**

Independent central core laboratories or expert physician(s) will conduct objective evaluations of remote monitoring tracings, Holter, Cerebral MRI, endoscopy and will evaluate PV stenosis of all subjects enrolled in Wave I (independently of symptoms) and symptomatic subjects of Wave II.

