
Stroke/Cerebrovascular Accident (CVA)
	
Diagnosis:
 
 
-Rapid onset of a focal or global neurological deficit with at least one of the following: change in level of consciousness, hemiplegia, hemiparesis, numbness or sensory loss affecting one side of the body, dysphasia or aphasia, hemianopia, amaurosis fugax, or other neurological signs or symptoms consistent with stroke.
 
-Duration of a focal or global neurological deficit <math>\geq 24</math> h; or <math>< 24</math> h, if therapeutic intervention(s) were performed (e.g. thrombolytic therapy or intracranial angioplasty); OR available neuroimaging documents a new hemorrhage or infarct; or the neurological deficit results in death.
 
-No other readily identifiable non-stroke cause for the clinical presentation (e.g., brain tumor, trauma, infection, hypoglycemia, peripheral lesion, pharmacological influences). †
 
-Confirmation of the diagnosis by at least one of the following: Neurology or neurosurgical specialist; Neuroimaging procedure (MR or CT scan or cerebral angiography); Lumbar puncture (i.e., spinal fluid analysis diagnostic of intracranial hemorrhage).
 
 
Definition:
 
Stroke: (diagnosis as above, preferably with positive neuroimaging study)
 
 
Minor—Modified Rankin score <math>< 2</math> at 30 and 90 days††
 
Major—Modified Rankin score <math>\geq 2</math> at 30 and 90 days
 

Primary Adverse Event	Description / Criteria
Transient Ischemic Attack	New focal neurological deficit with rapid symptom resolution (usually 1 to 2 h), always within 24h; neuroimaging without tissue injury.
Phrenic Nerve Paralysis	Absent phrenic nerve function as assessed by a sniff test. A phrenic nerve paralysis is considered to be permanent when it is documented to be present 12 months or longer following ablation.
Pulmonary Vein Stenosis*	A reduction of the diameter of a PV or PV branch. Severe PV stenosis ( $\geq 70\%$ reduction in the diameter of the PV) will be considered a PAE and major complication of AF ablation.

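### Severe PV stenosis counts as a primary adverse event with or without symptoms, but Wave II schedules post-procedure PV imaging only for symptomatic subjects, and the safety analysis does not allow for the difference

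*Protocol*

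**What the plan says.** **Definition.** Protocol Table 6 (15.1.3) states that severe stenosis, a "reduction in the diameter of the PV) will be considered a PAE and major complication of AF ablation". No symptom is required. The footnote to the endpoint removes the 7-day limit: device- or procedure-related death, "pulmonary vein stenosis and atrio-esophageal fistula that occur greater than one week (7 days) post-procedure are considered and analyzed as PAEs". Symptomatic disease is listed separately among the additional safety endpoints (8.2.3): "Occurrence of clinically symptomatic severe PV stenosis as documented by CT/MRA". Table 6 does remove silent events where that was intended, since asymptomatic cerebral embolism is expressly not a PAE. Stenosis has no such exception.

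**Ascertainment.** All subjects have a baseline cardiac CT/MRA. After the procedure, Wave I repeats it at 3 months. The Protocol Summary (Section 5, Study Design) gives Wave II the Wave I schedule "excluding the additional neurological, and post procedural PV (unless symptomatic) and esophageal assessments". For Wave II, Protocol 14.3 says it "is only required to be performed if subject presents with symptoms of PV stenosis". Under Protocol 14.6 the core laboratories or expert readers will "evaluate PV stenosis of all subjects enrolled in Wave I (independently of symptoms) and symptomatic subjects of Wave II".

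**Analysis.** Protocol 8.2: "Only Wave II subject data will be used for the purpose of primary hypothesis testing". The rule is Pr(p_S < 0.14) > 0.975 with a Beta(1,1) prior. Wave II SAP 7.4.1.1 says the primary safety outcome is known for all subjects at the early-success analysis. SAP 7.4.3 defines a missing safety outcome by follow-up time only (less than 3 months and no PAE). The best-case, worst-case and tipping-point analyses apply to those missing outcomes.

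**The concern.** The endpoint definition and the surveillance do not match. One component of the composite is defined by a diameter measurement, and most Wave II subjects need never have that measurement after the procedure. The SAP nevertheless treats the component as fully observed. A subject who was never re-imaged counts as a non-event rather than as unascertained, so no planned sensitivity analysis reaches that subject.

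The direction of any error is fixed. In a single-arm comparison with a fixed goal, no concurrent arm shares the under-ascertainment, and each missed case moves the result towards success. What is at stake is what the safety claim means: a PAE rate below 14% for the composite as defined, or below 14% for the composite as clinically detected.

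**Working it through.** **1. Inputs.** Goal 14%; success if Pr(p_S < 0.14) > 0.975, prior Beta(1,1) (Protocol 20.4.4.3; SAP 7.4.1). Possible sample sizes 180, 255 and 330; assumed true PAE rate 7%; safety dropout 5% (SAP Appendix I, 10.2). Neither document gives a rate of undetected asymptomatic severe stenosis. Call it *h*: the proportion of subjects whose only PAE is an undetected severe stenosis. It is an assumption throughout.

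**2. The plan's own power.** For *n* evaluable subjects, find the largest *y* with Pr(p < 0.14 | Beta(1+y, 1+n−y)) > 0.975, then take P(Y ≤ y) for Y ~ Binomial(n, 0.07). Averaging over 5% random dropout gives 0.8255, 0.9396 and 0.9818 at N = 180, 255 and 330. Weighting by the stopping proportions in Table 3.a at 65% effectiveness:

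0.5535 × 0.8255 + 0.2854 × 0.9396 + 0.1611 × 0.9818 = 0.883

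The plan states 0.8853, so the rule is reproduced.

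**3. Pass limits.** At n = 171 (180 × 0.95), 15 events pass (posterior probability 0.9755) and 16 fail (0.9575). At n = 314 (330 × 0.95 = 313.5), 31 pass (0.9829) and 32 fail (0.9739).

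**4. False pass on the endpoint as defined.** Let the true rate be exactly 14%, with *h* unseen. Recorded events then follow Binomial(n, 0.14 − h), and the false-pass probability is P(Y ≤ limit):

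| *h* (assumed) | n = 171 | n = 314 |
|---|---|---|
| 0 | 2.6% | 1.8% |
| 1 point | 5.8% | 5.5% |
| 2 points | 11.6% | 14.1% |

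The 2.6% in the top row reflects discreteness at exactly 171. Averaged over random dropout at N = 180 / 255 / 330, the figures are 2.1 / 2.1 / 2.2% at h = 0, then 2.6 / 2.7 / 2.9% at 0.25 points, 4.7 / 5.5 / 6.4% at 1 point and 9.7 / 12.6 / 15.9% at 2 points. A larger sample does not remove the effect.

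**5. What an extended tipping point would show.** Suppose 12 PAEs are recorded in 171 (7.0%). The posterior probability is 0.997. Three undetected cases bring the count to 15, which still passes; a fourth brings it to 16, which fails. The tipping point is 4 cases, 4/171 = 2.3%. With 22 in 314 (7.0%) it is 32 − 22 = 10 cases, 10/314 = 3.2%.

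**6. Can Wave I settle it?** With no severe stenosis among 35 imaged subjects, the one-sided 95% upper bound is 1 − 0.05^(1/35) = 8.2%; among 40 it is 7.2%. At a true rate of 2%, the chance of seeing at least one case is 1 − 0.98^35 = 51%, or 55% with 40. Wave I is relevant context but too small to exclude rates at the tipping point.

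**The case against.** **The effect may be nil.** Protocol 6.4.1 says PV stenosis has not been reported after pulsed field applications. This stands. The same paragraph calls the risk with this energy unknown, so zero is possible but not established. A reader might take the figure of under 4% in that paragraph as an estimate of what Wave II misses. It is not one: it concerns PV stenosis in radiofrequency procedures, with no severity grade and no split by symptoms.

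**The goal may share the same surveillance.** The 14% comes from complication rates in five earlier trials (7%, upper bound 8%, plus 6 points; Protocol 6.3). If those trials also found stenosis through symptoms, Wave II is compared like with like, and imaging everyone would make it stricter than its goal. The documents do not say how those trials ascertained stenosis, so neither this defence nor its opposite can be checked.

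**Detection is limited, not impossible.** One might infer that Wave II cannot see asymptomatic stenosis at all, or that the PAE component and the symptomatic additional endpoint are identical there. Neither follows. Imaging is only not required; a severe stenosis found incidentally, for example around a repeat ablation, is reportable, meets Table 6 and counts.

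**The design is open and staged.** Symptom-driven imaging in Wave II is stated in several places, and systematic imaging is assigned to Wave I as the safety-characterisation phase. This is a fair answer to any suggestion of concealment. It does not answer the SAP's statement that the outcome is known for everyone, or the absence of a sensitivity analysis.

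**Conclusion.** The point holds as a mismatch between definition, ascertainment and analysis in the current text. Severe PV stenosis is a PAE regardless of symptoms or timing; Wave II looks for it only on symptoms; and SAP 7.4.1.1 and 7.4.3 handle the component as if it were fully observed. Any missed case can only lower the observed PAE rate.

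The size is not known. The false-pass figures of 5.8% and 11.6% (n = 171), or 5.5% and 14.1% (n = 314), rest on assumed unseen rates of 1 and 2 points, on a true as-defined rate of exactly 14%, and on reading the goal as applying to the literal Table 6 definition. They show sensitivity and do not estimate the trial's error rate. Two stronger conclusions are tempting: that the trial understates its PAE rate, and that its type I error exceeds the 2.5% claimed in SAP Section 4. The documents support neither without a known rate of undetected stenosis and knowledge of how the source trials imaged their subjects.

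**What to change.** 1. **Keep the Table 6 definition.** Restricting the Wave II component to symptomatic stenosis would make definition and surveillance agree, but would drop incidentally detected asymptomatic cases that now count and would narrow a pre-specified composite.
2. **Correct Wave II SAP 7.4.1.1.** State that PV stenosis in Wave II is clinically ascertained (imaging on symptoms or incidental), so the outcome is not known for all subjects on this component. Word the Wave II safety conclusion the same way.
3. **Extend the tipping-point analysis in SAP 7.4.1.1 and 7.4.1.2** to subjects without post-procedure PV imaging. Report how many there are, and the number and rate of undetected severe stenoses at which Pr(p_S < 0.14) falls to 0.975 or below. Show this beside the Wave I 3-month CT/MRA rate with its exact interval.

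The cost is a few lines of text and programming and a slightly more qualified safety claim. It needs no additional imaging and no change to the visit schedule.
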